#### 4.1.1. Design Overview

In this study, 32 eligible subjects will be randomized in a 1:1 ratio to 1 of 2 treatment groups; 16 subjects in Treatment Group A and 16 subjects in Treatment Group B.

At the beginning of the Screening Period, subjects will sign the informed consent form (ICF). During the 21-day Screening Period, subjects' eligibility will be confirmed. They will undergo medical history evaluation, physical examination, vital sign determination, ECGs, and clinical laboratory assessments.

During the Treatment Period, subjects will receive study drug in the assigned treatment group.

Treatment Group A: On Day 1, subjects will begin a regimen of 600-mg efavirenz tablet once daily and will continue the regimen through Day 35. Efavirenz will be taken before bedtime on an empty stomach (no food for at least 2 hours before and after dosing). On Day 15, subjects will receive a single dose of 60-mg quizartinib ( $2 \times 30$  mg), which will be administered with 240 mL of water after at least 10 hours of fasting. Quizartinib will be taken in the morning. Subjects will continue to fast for 4 hours postdose. Pharmacokinetic blood samples will be collected from Day 15 through Day 36. Subjects will be discharged from the CRU and from the study at end-of-study (EOS) on Day 36 after study procedures are completed. Safety assessments will be conducted from Day 1 through Day 36.

Treatment Group B: On Day 1, subjects will be given a single dose of 60-mg quizartinib ( $2 \times 30$  mg) with 240 mL of water after 10 hours of fasting. Quizartinib will be taken in the morning followed by an additional 4 hours of fasting. Pharmacokinetic blood samples will be collected from Day 1 through Day 22. Subjects will be discharged from the CRU and from the study at EOS on Day 22 after study procedures are completed. Safety assessments will be conducted from Day 1 through Day 22.

After study treatment is discontinued, subjects will be followed for 30 days for safety.

The subject population is described in Section 5. A flow diagram of study activities is presented in Figure 1.1.

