### **9.5.2. Safety Analysis**

#### **9.5.2.1. Adverse Events**

Treatment-emergent adverse events (TEAEs) are defined as new AEs that occur after the first dose of study drug. AEs collected 30 days after the last dose of study drug will not be considered

TEAEs unless they are treatment-related. AEs will be coded using the MedDRA dictionary. An AE will be assigned to the study day in which it started, even if it resolved on a subsequent day. The incidence of TEAEs will be summarized by treatment group. The number and percentage of subjects reporting TEAEs will be calculated overall, by system organ class, by preferred term, and by treatment group.

Treatment-emergent adverse events will be further summarized by CTCAE grade and relationship to study drug or AEs that were present prior to the first dose but which worsened in severity after the first dose of study drug. Similarly, the number and percentage of subjects reporting treatment-emergent SAEs and related treatment-emergent SAEs will be tabulated, treatment-emergent AESIs, and TEAEs leading to discontinuation of study drug.

A by-subject AE (including treatment-emergent) data listing including but not limited to verbatim term, preferred term, system organ class, CTCAE grade, and relationship to study drug will be provided. Deaths, SAEs, AESIs, and AEs associated with study drug discontinuation will be listed.

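### Adverse event tables by treatment group mix about 14 efavirenz-only days into Group A and compare 36 days of observation with 22

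*Combined protocol and SAP*

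**What the plan says.** Section 9.5.2.1 sets the rule for the adverse event tables:

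- **Start of counting.** TEAEs are "defined as new AEs that occur after the first dose of study drug". Table 6.1 lists both quizartinib and efavirenz as study drugs.
- **End of counting.** "AEs collected 30 days after the last dose of study drug will not be considered" treatment-emergent, unless they are related to treatment.
- **Tabulation.** "The incidence of TEAEs will be summarized by treatment group", and "The number and percentage of subjects reporting TEAEs will be calculated overall, by system organ class, by preferred term, and by treatment group".
- **Further breakdown.** "Treatment-emergent adverse events will be further summarized by CTCAE grade and relationship to study drug".
- **Onset.** "An AE will be assigned to the study day in which it started".

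The section names no onset period as a table column and no exposure-time denominator.

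The dosing schedule comes from Section 4.1.1 and Table 1.1. Group A takes efavirenz on Days 1 to 35 and a single quizartinib dose on the morning of Day 15. Group B takes a single quizartinib dose on Day 1. For Group A, "Safety assessments will be conducted from Day 1 through Day 36"; for Group B, "Safety assessments will be conducted from Day 1 through Day 22".

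Section 3.2 gives the secondary objective as the safety and tolerability of quizartinib given alone and given together with efavirenz. Section 9.1 states that the study does not test hypotheses. Section 9.5 describes itself as a summary and leaves detail to a SAP to be finalised before database lock. That SAP is not part of the available document.

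**The concern.** The two columns of the TEAE table do not describe the two conditions named in the objective. Group B's column is quizartinib alone over 22 days. Group A's column is an efavirenz-only lead-in followed by quizartinib with efavirenz, over 36 days. An event on Day 5 in Group A, before any quizartinib, counts in the column that will be read as quizartinib with efavirenz.

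The lead-in events and the longer observation both tend to raise the crude percentage in Group A. A reader could take the difference as poorer tolerability of the combination when adding efavirenz to quizartinib changed nothing. The denominator has a related problem. The Safety Population (Section 9.4.2) requires one dose of any study drug, so a Group A subject who leaves during the lead-in is counted there without having received quizartinib.

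What is at stake is the reading of a descriptive safety table. No test and no pharmacokinetic comparison depends on it.

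**Working it through.** **Inputs from the document.** Safety assessment runs over Days 1–36 in Group A and Days 1–22 in Group B (Section 4.1.1). Efavirenz is given on Days 1–35 and quizartinib on Day 15 in Group A; quizartinib is given on Day 1 in Group B (Tables 1.1 and 1.2). Each group has 16 subjects. The last pharmacokinetic sample is 504 hours after quizartinib in both groups. The document gives no expected adverse event rates for this study, so the rates below are assumptions.

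**Step 1: the plan's own durations.** Screening, check-in day and treatment days add to 21 + 1 + 36 = 58 days in Group A and 21 + 1 + 22 = 44 days in Group B. These match the durations in Section 4.1.4 and show that they stop at end of study.

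**Step 2: length of the two columns.**

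- To end of study: 36 / 22 = 1.64.
- Share of Group A's days before quizartinib: 14 / 36 = 39%.
- Elapsed time from first dose to the 504-hour sample, assuming efavirenz at 22:00 and quizartinib at 08:00: 13.4 + 21.0 = 34.4 days against 21.0 days, again 1.64. For efavirenz between 20:00 and 24:00 and quizartinib between 07:00 and 10:00, the ratio is 1.63 to 1.65.

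**Step 3: whether the 30-day rule evens this out.** It does not. On paper it ends at Day 35 + 30 = 65 in Group A and Day 1 + 30 = 31 in Group B, which widens the gap. How far events after end of study would be collected in practice is uncertain, because no visit is scheduled then. Only 36 against 22 days is relied on here.

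**Step 4: illustration with an equal constant event rate.** If a proportion p of Group B has at least one event in 22 days, the same rate over 36 days gives 1 − (1 − p)^(36/22).

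| Group B, 22 days | Group A, 36 days, no effect of co-administration |
|---|---|
| 10% | 15.8% |
| 30% | 44.2% |
| 50% | 67.8% |

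At 30% this is 16 × 0.30 = 4.8 subjects against 16 × 0.442 = 7.1.

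**Step 5: illustration without a constant rate.** Suppose 30% have an event in the 22 days after quizartinib in both groups, and a share q of Group A has one in the lead-in, independently of later events. Group A's column then reads 1 − 0.70 × (1 − q).

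| q | Group A column | Group B column |
|---|---|---|
| 0% | 30% | 30% |
| 10% | 37% | 30% |
| 20% | 44% | 30% |
| 30% | 51% | 30% |

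**Step 6: the aligned comparison.** From the quizartinib dose to end of study, Group A covers Days 15–36 and Group B Days 1–22. That is 22 study days each, a ratio of 1.0.

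**The case against.** The strongest reply is that silence in a summary is being read as a plan. Section 9.5 defers to a SAP, and column layout is ordinary SAP content. This stands as a limit: a split could still be added there. But Section 9.5 describes the SAP as covering populations and the handling of missing, unused and spurious data. It promises no onset split, and the rule in Section 9.5.2.1, followed exactly, gives the unaligned table.

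Second, Section 10.4.5 classifies causality in Group A as efavirenz alone or the combination, and TEAEs are to be summarised by relationship. This helps in part. It separates only events judged related, rests on investigator judgement in an open-label study, and does not equalise time.

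Third, the study is descriptive, no formal between-group safety comparison is planned, and reporting everything that happened on the assigned regimen is legitimate. That is a reason to keep a whole-study column, but not to make it the only one, given what the objective asks.

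Fourth, the other safety endpoints are largely aligned. ECGs and vital signs are taken at the same times relative to quizartinib. Post-quizartinib hematology and chemistry fall on Days 19, 27 and 36 in Group A and Days 5, 13 and 22 in Group B, so 4, 12 and 21 days after the dose in both. This is correct and confines the point to the TEAE tables.

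Fifth, the percentages in Steps 4 and 5 are hypothetical, and at q = 0 there is no distortion from the lead-in. That also stands; only the day counts are firm.

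**Conclusion.** The concern holds. As written, the TEAE tables set an efavirenz lead-in plus combination column of 36 days beside a quizartinib-alone column of 22 days. The ratio is 1.64, and 39% of Group A's days precede quizartinib. These figures come directly from the schedule.

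The direction of the distortion, towards higher percentages in Group A, follows whenever events occur in the lead-in among subjects who have none later. Its size depends on event rates that the document does not give; 30% appearing as about 44% illustrates a plausible scale and is not a forecast.

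The effect is limited to interpretation of a descriptive secondary endpoint. The change should be made before database lock.

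**What to change.** In Section 9.5.2.1, or in the SAP before database lock, specify three summaries:

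1. **Lead-in (Group A only):** events with onset from the first efavirenz dose to just before the quizartinib dose.
2. **After quizartinib (both groups):** events starting or worsening from the quizartinib dose to end of study, with quizartinib-dosed subjects as denominator. This covers Days 15–36 in Group A and Days 1–22 in Group B.
3. **Whole study (both groups):** all TEAEs under the present definition, so that lead-in events, early withdrawals and events after end of study are still counted.

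No new data, visits or subjects are needed, since the onset day is already assigned. The cost is wording, programming and somewhat longer tables.

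Three limits should be noted beside the tables. The second summary still includes concurrent efavirenz in Group A, so it aligns time without isolating quizartinib. It omits subjects who left during the lead-in. It also omits lead-in events that persist without worsening. The last two could make Group A look better tolerated in that column, which is why the first and third summaries should be shown with it.

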#### **9.5.2.2. Clinical Laboratory Evaluation**

Descriptive statistics will be provided for the clinical laboratory results by scheduled time of evaluation and by treatment group, as well as for the change from baseline. The baseline value is defined as the last non-missing value before the initial administration of study drug. In addition, mean change from baseline will be presented by treatment group for the maximum and minimum post-treatment values and the values at the EOS.

Abnormal clinical laboratory results will be graded according to NCI-CTCAE version 5.0, if applicable, and the grade will be presented in a by-subject data listing. A shift table, presenting by treatment group the two-way frequency tabulation for baseline and the worst post-treatment value according to the CTCAE grade, will be provided for clinical laboratory tests. A listing of abnormal clinical laboratory test results deemed of clinical significance or of Grade 3 or 4 will be generated.

#### **9.5.2.3. Electrocardiograms**

Descriptive statistics will be provided for the ECG measurements by scheduled time of evaluation and by treatment group, as well as for the change from baseline. The baseline value is defined as the last non-missing value before the initial administration of study drug. In addition, the number and percentage of subjects with ECG interval values meeting the criteria will be tabulated (e.g., QTc  $\leq$ 450 ms, >450 to  $\leq$ 480 ms, >480 ms to  $\leq$  500 ms, and >500 ms).

A listing of ECG data will be generated.

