- c A full physical examination that includes an evaluation of the head, eyes, ears, nose, and throat and the cardiovascular, dermatological, musculoskeletal, respiratory, gastrointestinal, and neurological systems will be performed at Screening, and on Day -1, Day 14, and EOS.
- d BMI at Screening only
- e Female subjects (WOCBP only)
- f Naturally postmenopausal female subjects only
- g Blood samples for hematology and serum chemistry will be collected after a 10-hour fast at Screening, and on Day -1, Day 7, predose (quizartinib) on Day 15, and on Day 19, Day 27, and EOS.
- h Triuplicate ECG (approximately 2 minutes apart) and after at least 5 minutes of quiet rest in the supine position. When a blood collection is scheduled concomitantly with an ECG, the ECG should be taken at least 5 minutes prior to the blood collection and at predose, 2, 4, and 8 hours after quizartinib administration.
- i Vital signs will be taken after at least a 5-minute supine rest; vital signs should be taken at all ECG timepoints.
- j Efavirenz will be dosed as 600 mg once daily from Day 1 through Day 35. Efavirenz will be taken before bedtime on an empty stomach (no food for at least 2 hours before and after dosing).
- k A single dose of 60-mg quizartinib (2 × 30 mg) will be administered following an overnight fast of 10 h on Day 15. Water consumption will be restricted from 1 hour predose to 2 hours postdose, except for the 240 mL of water that is to be administered with quizartinib. Subjects will continue to fast for 4 hours postdose.
- l Day 15 through 36 (relative to quizartinib) PK samples for quizartinib will be collected at predose, 1, 2, 4, 6, 8, 12, 24, 48, 72, 96, 144, 216, 288, 360, 432, and 504 hours post-quizartinib dose. Quizartinib and AC886 showed temperature- and concentration-dependent partitioning into blood cells; therefore, blood samples must be processed at room temperature for determination of plasma quizartinib and AC886 concentrations.

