#### **3.2. Secondary Objective /Endpoint**

The secondary objective of this study is:

- To assess the safety and tolerability of quizartinib in healthy subjects when administered alone and when co-administered with efavirenz.

The secondary endpoints of this study are:

- Treatment-emergent adverse events (TEAEs), vital signs, 12-lead electrocardiograms (ECG), clinical laboratory tests (chemistry, hematology, coagulation, and urinalysis), and physical examinations.

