## 6. STUDY TREATMENT(S)

### 6.1. Study Drug(s) Description

Table 6.1: Study Drug Dosing Information

Study Drug Name	Quizartinib	Efavirenz
Dosage Formulation	30-mg tablet a	600-mg tablet
Dosage Level(s)	60 mg	600 mg
Route of Administration	Oral	Oral
Dosing	Single dose	Once daily
Duration	Once	Once daily for 35 doses
Packaging	High-density polyethylene (HDPE) bottles of 30 tablets  Packaging will clearly display the name of product, storage condition, and other required information as applicable in accordance with local regulations	Bottles of 30 tablets
Labeling	Bottles will be labeled as required per local and regulatory requirements	Bottles will be labeled as required per local and regulatory requirements

a Each 30-mg tablet contains 30-mg quizartinib dihydrochloride (26.5 mg free base).

Quizartinib will be supplied by the Sponsor, and efavirenz will be supplied by Worldwide Clinical Trials (Worldwide).

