#### **9.5.2.4. Vital Signs**

Descriptive statistics will be provided for the vital sign measurements by scheduled time of evaluation and by treatment group, as well as for the change from baseline. The baseline value is defined as the last non-missing value before the initial administration of study treatment. A listing of vital sign data will be generated.

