#### **10.4.5. Causality Assessment**

The Investigator should assess causal relationship between an adverse event and the study drug based on his/her clinical judgment and the following definitions. The causality assessment must be made based on the available information and can be updated as new information becomes available.

- Related:
  - The AE follows a reasonable temporal sequence from study drug administration and cannot be reasonably explained by the subject's clinical state or other factors (e.g., disease under study, concurrent diseases, and concomitant medications).  
or
  - The AE follows a reasonable temporal sequence from study drug administration and is a known reaction to the drug under study (or its chemical group) or is predicted by known pharmacology.

- Not Related:
  - The AE does not follow a reasonable sequence from study drug administration or can be reasonably explained by the subject's clinical state or other factors (e.g., disease under study, concurrent diseases, and concomitant medications).

Determinations of causality for Treatment Group A will be categorized as follows:

- Efavirenz when administered alone
- Efavirenz and quizartinib when administered in combination

Determinations of causality for Treatment Group B will be categorized as follows:

- Quizartinib when administered alone

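### The safety sections define one baseline, before the first study drug, so Group A's changes after quizartinib start 15 days and 14 efavirenz doses earlier and are not like for like with Group B's

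*Combined protocol and SAP*

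**What the plan says.** For ECGs, Section 9.5.2.3 states: "The baseline value is defined as the last non-missing value before the initial administration of study drug". Section 9.5.2.2 uses the same definition for laboratory tests. Section 9.5.2.4 does so for vital signs with a small change of wording ("before the initial administration of study treatment"). No second baseline appears in any of the three.

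All three sections summarize change from this baseline descriptively, by visit and by arm. For laboratory tests there are two further summaries: "mean change from baseline will be presented by treatment group for the maximum and minimum post-treatment values and the values at the EOS", and a shift table giving "the two-way frequency tabulation for baseline and the worst post-treatment value according to the CTCAE grade".

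Table 6.1 lists both quizartinib and efavirenz as study drugs, with efavirenz given "Once daily for 35 doses". Group A takes efavirenz at bedtime from Day 1 and receives quizartinib on the morning of Day 15. Group B receives quizartinib on the morning of Day 1 and nothing else.

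The secondary objective (Section 3.2) is "To assess the safety and tolerability of quizartinib in healthy subjects when administered alone and when co-administered with efavirenz". For adverse events in Group A, Section 10.4.5 separates causality under efavirenz alone from causality under "Efavirenz and quizartinib when administered in combination".

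**The concern.** In Group B the rule gives a baseline taken just before quizartinib. In Group A it gives one taken before two weeks of another drug. A Group A change at, say, 4 hours after quizartinib therefore contains whatever efavirenz and confinement did between Day -1 and Day 15, and Group B has no such component. A real quizartinib difference between arms could be hidden, or an apparent one created.

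ECG change is where this matters most. Section 2.3 names QT prolongation as an event of special interest with a dose-dependent link to quizartinib, and reports earlier experience partly as QTcF increase from baseline. Section 4.2 expects CYP3A induction to lower quizartinib exposure, so the two arms may well differ.

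The laboratory extremes raise a separate issue. Group A samples drawn after efavirenz starts but before quizartinib can supply the maximum, minimum or worst grade. Group B has no equivalent samples.

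**Working it through.** **Inputs.** Dosing days and times come from Tables 1.1, 1.2 and 6.1. In Group A, hematology and chemistry are drawn at Screening and then "on Day -1, Day 7, predose (quizartinib) on Day 15, and on Day 19, Day 27, and EOS". Table 1.2 gives Group B's draws as Day -1, Day 5, Day 13 and EOS. Coagulation, urinalysis, ECG and vital-sign days are read from the table rows. Table 1.1 schedules no ECG or vital signs on Days 1 to 14, so Group A's last values before efavirenz are those of Day -1.

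**Day count.** There is no Day 0: 504 h = 21 days, which takes Day 1 to Day 22 and Day 15 to Day 36, as the tables show.
- Day -1 to Day 15: 1 + 14 = 15 days.
- Day -1 to Day 1: 1 day.
- Bedtime efavirenz on Days 1 to 14: 14 doses before the Day 15 morning dose. This reproduces the 14-day lead-in of Section 4.2. Table 1.1 marks efavirenz in both Day 15 columns, but bedtime dosing and a total of 35 doses over 35 days support 14.

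| Assessment | A: baseline to quizartinib | B: baseline to quizartinib | Excess in A |
|---|---|---|---|
| ECG, vital signs, coagulation | 15 days | 0 days (Day 1 predose) | 15 days |
| Hematology, chemistry, urinalysis | 15 days | 1 day (Day -1) | 14 days |

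**What the Group A change contains.** For a subject with value Y at time t:

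Y(t) − Y(Day -1) = [Y(t) − Y(Day 15 predose)] + [Y(Day 15 predose) − Y(Day -1)]

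The second bracket is efavirenz plus time. With complete data its mean can be subtracted using the by-visit means. The spread of the first bracket cannot be obtained that way: its variance needs the covariance of the two tabulated changes, which is not reported.

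**Post-baseline laboratory draws by schedule.**

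| Test | Group A | Group B |
|---|---|---|
| Hematology, chemistry | Days 7, 15 predose, 19, 27, EOS = 5 | Days 5, 13, EOS = 3 |
| Coagulation | Day 15 predose, Day 19, EOS = 3 | Day 5, EOS = 2 |
| Urinalysis | Day 19, EOS = 2 | Day 5, EOS = 2 |

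Relative to quizartinib, Group A's hematology and chemistry draws fall at −8, 0 (predose), +4, +12 and +21 days, and Group B's at +4, +12 and +21. Dropping the two earlier Group A draws makes the arms match exactly.

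**Effect of the extra draws alone.** Assume normal values, no drug effect and equal correlation ρ between a subject's visits. The expected maximum of k values is E_k × √(1−ρ) in SD units, with E_2 = 0.564, E_3 = 0.846 and E_5 = 1.163. The shared baseline does not alter the difference between arms.

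| Comparison | ρ = 0 | ρ = 0.5 | ρ = 0.75 |
|---|---|---|---|
| 5 vs 3: (1.163 − 0.846) × √(1−ρ) | 0.317 | 0.224 | 0.158 |
| 3 vs 2: (0.846 − 0.564) × √(1−ρ) | 0.282 | 0.199 | 0.141 |

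Simulating the maximum change from baseline (1,000,000 subjects per cell) gave 0.317, 0.225, 0.159 and 0.282, 0.199, 0.142. The minimum is the mirror image. On matched visits every gap is 0. The documents do not give ρ, so the range is illustrative.

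**The case against.** A baseline before any study drug is conventional, and for the efavirenz-plus-quizartinib regimen as a whole it is the right one. Re-basing to Day 15 would remove any efavirenz contribution. This stands, and it is why that baseline should stay.

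Section 9.5 calls itself a summary and promises a SAP before database lock, where a second baseline could be added. That is a fair route to the fix. But the section states a definite rule, and nothing in the supplied text adds to it.

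Section 9.1 disclaims hypothesis testing, and only PK parameters are formally compared between arms. That limits the consequence. Yet the safety tables are laid out by arm to serve an objective that names quizartinib with and without efavirenz, so readers will set the columns side by side.

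Much can be recovered. Day 15 predose is a scheduled time, so its mean change from Day -1 will be tabulated where measured, and the ECG and vital-sign listings allow subject-level derivation. Laboratory grades are also to be listed by subject, but the listing's columns are not specified and it does not replace a shift table.

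The causality categories in Section 10.4.5 concern adverse events and impose no baseline rule. They show only that the protocol already separates the two periods elsewhere.

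Two limits of size also stand. The documents give no efavirenz effect on any of these measures, so the baseline distortion could be small. The SD figures concern only the extra draws, and they assume that the undefined post-treatment period begins with the first study drug.

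**Conclusion.** The concern holds. Under the stated rule, Group A's baseline precedes quizartinib by 15 days and 14 efavirenz doses, against 0 or 1 day and no efavirenz in Group B. The resulting bias in mean change cannot be computed from the documents. The extra laboratory draws add up to about a third of an SD to Group A's expected maximum for hematology and chemistry, and about half that at a within-subject correlation of 0.75. This rests on the natural reading that every draw after the first study drug counts as post-treatment.

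The reach is limited to descriptive secondary tables: the spread of paired changes after quizartinib, and the laboratory extremes and grade shifts. The absolute QTc categories, the Hy's Law criterion, the 480 ms monitoring trigger and the primary PK analysis do not use this baseline. It should be corrected before database lock, but it does not threaten the study's main result.

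**What to change.** Keep the pre-first-dose baseline for whole-regimen summaries, and add the following to the SAP (and to Section 9.5.2 if it is amended):

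- A pre-quizartinib baseline for changes after quizartinib in ECG, vital signs, hematology, chemistry and coagulation: the last non-missing value before that dose. This is Day 15 predose in Group A, and Day 1 predose in Group B, or Day -1 where no Day 1 sample is scheduled.
- Between-group laboratory maximum, minimum and shift tables restricted to matched visits. For hematology and chemistry these are Days 19, 27 and EOS in A against Days 5, 13 and EOS in B. For coagulation they are Day 19 and EOS against Day 5 and EOS.
- A separate Group A summary of the efavirenz-alone period, from Day -1 through Day 15 predose and including the Day 7 laboratory draw, so that no on-treatment value is lost.
- A note that urinalysis keeps Day -1, because Group A has no sample between Day -1 and Day 19.
- A statement that re-based Group A changes still include continuing efavirenz exposure through Day 35.

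The cost is wording, one derived baseline variable and a few extra tables. No new assessment is needed.
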